#### ***Treatment Procedures: Investigational (Superion® ISS) and Control (X-STOP® IPD®) groups***

Surgical procedure:

- Follow the applicable surgical procedure: Superior® ISS Surgical Technique Manual or X-STOP® IPD® Surgical Technique Manual (Manufacturer's Instructions)
- Perform the procedure under fluoroscopic guidance
- Surgery under local anesthesia with or without conscious sedation is recommended. General anesthesia is allowed at the discretion of the Investigator.

The following information was collected at the time of surgery:

- Date of admission
- Date of surgery
- Type of anesthesia
- Level(s) treated
- Device information
- Operative time
- Estimated blood loss
- Intra-operative adverse events

### 6.5.4 Post-Procedure Visits

***The following was collected at the Discharge Assessment for treated patients (0-7 days)***

Most patients were discharged the day of procedure. If clinically indicated, some patients stayed for up to 23 hours or were admitted based on co-morbid conditions.

Discharge Assessment: 

• Visual Analogue Scale (VAS) to assess leg and back pain

• Medical treatment

• Adverse event

• Concomitant medication and treatment

• Length of hospital stay

• Type of anesthesia

Neurological Assessment: 

• Muscle strength

• Sensory and Reflexes

• Range of motion

• Palpation of pulses

• Straight leg raise

• Femoral Stretch

Radiographic studies: 

• Standing Anterior/Posterior Lumbar Spine X-ray

• Lateral Lumbar Spine X-ray

***The following information was/will be collected at the Follow-up Visits for treated patients at 6-week ( $\pm 2$  weeks), 3-month ( $\pm 2$  weeks), 6-month ( $\pm 1$  month), 12-month ( $\pm 2$  months), 18-month ( $\pm 2$  months), 24-month ( $\pm 2$  months), and will be collected annually ( $\pm 3$  months) thereafter through 60 months as required by this protocol:***

Subject Self-Report Questionnaires: 

• Zurich Claudication Questionnaire (ZCQ)

• Visual Analogue Scale (VAS)

• SF-12 version 2 Health Related Quality of Life

• Oswestry Disability Index (ODI)

• VertiFlex Patient Satisfaction Questionnaire

Neurological Assessment: 

• Muscle strength

• Sensory and Reflexes

• Range of motion

• Palpation of pulses

• Straight leg raise

• Femoral Stretch

Follow-up Assessment: 

• Work status and time to return to work or normal ADL (activities of daily living)

• Leg and back pain

• Medical treatment

• Adverse event

• Concomitant medication and treatment, including narcotic usage

Radiographic studies :

- Standing Anterior/Posterior Lumbar Spine X-ray
- Lateral Lumbar Spine X-ray
- Flexion/Extension Lateral Lumbar Spine X-rays

The Study Visit Schedule (**Appendix A**) provides an overview of activities to be performed at each annual study visit through 60 months.

## **7 Termination of Subject Participation**

Subjects may voluntarily withdraw from the study at any time for any reason. The Investigator(s) may elect to withdraw a subject from the study at any time due to lack of compliance or for any reason unrelated to the study treatment if such a decision is in the subject's best medical interest. If a subject withdraws from the study, or is withdrawn by the Investigator(s), as much follow-up data as possible will be obtained, particularly regarding possible adverse events. The primary reason for termination or discontinuation will be documented on the End of Study Case Report Form.

If the Investigator(s) reports a subject to be lost to follow-up, the monitor will ensure that documentation is complete regarding the reason(s) this has occurred and will ensure that every attempt is made by the Investigator(s) to contact the subject or significant other persons associated with the subject to determine subject status. Appropriate documentation will consist of at least two documented attempts at contact via telephone, followed by an attempt to contact via registered U.S. Mail.

## **8 Study Deviation**

A study deviation is defined as an event where the clinical investigator or site personnel did not conduct the study according to the Clinical Protocol or the Investigator Agreement. Deviations will be classified as follows:

Major Deviation: Any deviation from patient inclusion and exclusion criteria or patient informed consent procedures.

Minor Deviation: Deviation from a protocol requirement, such as incomplete or missed patient evaluations, follow-up performed outside specified time windows, etc.

Investigators will be required to obtain proper approval from the Sponsor before initiating major deviations from the Clinical Protocol, except where necessary to protect the life or physical well-being of a subject in an emergency. Such approval will be documented in writing and maintained in the study files. Although prior approval is generally not expected for minor deviation, the event must still be reported.

Deviations will be reported to the Sponsor regardless of whether medically justifiable, pre-approved by the Sponsor, or taken to protect the subject in an emergency. Subject-specific deviations will be reported on the Protocol Deviation CRF. Non-subject-specific deviations, (e.g. unauthorized use of a study device outside the study) will be reported in writing. Investigators will also adhere to procedures for reporting study deviations to their IRB in accordance with their specific IRB reporting policies and procedures.

## 9.0 Adverse Events

### 9.1 Definitions

An **Adverse Event (AE)** is any undesired clinical response or complication experienced by a subject. All operative and postoperative AEs, whether device-related or not, will be recorded on the AE Case Report Forms.

The Investigator, on the basis of his or her clinical judgment and the following definitions, will determine the severity of the AE and the relationship to the device and/or procedure:

- Not related: The AE is clearly not related
- Unknown/Undetermined: The AE is unknown or undetermined to be related
- Related: The AE is clearly related
  - Device related: The AE is related to the study device or the control device
  - Procedure related: The AE is related to the procedure to implant the study or control device

The **severity** of an AE may be mild, moderate or severe. Severity is determined by the Clinical Investigator, using the following definitions, and is not necessarily the subject's interpretation:

- Mild** The AE is transient or causes mild discomfort. There usually is no intervention/therapy required and the AE does not interfere with the subject's normal activities.
- Moderate** The AE causes some limitation in activity and some assistance may be needed. There is no or minimal medical intervention/therapy required.
- Severe** The AE causes marked limitation in activity. The subject's usual daily activity is interrupted. The subject may require medical intervention/therapy, hospitalization is possible.

The term "severe" is used to describe intensity (severity) of a specific event. An event itself may be of relatively minor medical significance (such as a severe headache). This is not the same as "serious", which is based on event outcomes or actions taken to prevent or treat an event and is usually associated with events that pose a threat to the patient's life or functioning.

The AE is regarded as a **Serious Adverse Event (SAE)** if the injury or illness:

- A) Results in death
- B) Is life-threatening,
- C) Results in or prolongs hospitalization
- D) Results in permanent impairment of a body function or permanent damage to a body structure, or
- E) Necessitates medical or surgical intervention to preclude permanent impairment of a body function or permanent damage to a body structure.

A **Serious Adverse Device Effect (SADE)** is a device related adverse event that has resulted in any of the consequences characteristic of a serious adverse event or that might have led to any of these consequences if suitable action had not been taken or intervention had not been made.

An **Unanticipated Adverse Device Effect (UADE)** is any serious adverse effect on health or safety, any life-threatening problem or death caused by, or associated with a device, if that effect, problem, or death was not previously identified in nature, severity, or degree of incidence in the Risks identified for the study or control device; or any other unanticipated serious problem associated with a device that relates to the rights, safety, or welfare of subjects.

The Sponsor's Clinical Research group must be notified of all **Unanticipated Adverse Device Effects** and **Serious Adverse Device Effects** within 24 hours at:

## 9.2 Anticipated Adverse Events

All AEs identified for the study or control device in Section 12 are considered 'anticipated'.

## 9.3 Subsequent Surgical Interventions

If the patient requires a subsequent surgical intervention at the index level(s), the Investigator should exit the patient from the study and document the reason on the End of Study CRF. The patient should be followed until discharge from post-operative care or resolution of any adverse events up to a maximum of 30 days. Subsequent surgical interventions are defined as:

- A revision is a procedure that adjusts or in any way modifies or removes part of the original implant configuration, with or without replacement of a component. A revision may also include adjusting the position of the original configuration.
- A removal is a procedure where all of the original system configuration are removed with or without replacement.

- A reoperation is any surgical procedure at the involved level(s) that does not include removal, modification, or addition of any components to the system.
- A supplemental fixation is a procedure in which additional instrumentation not under study in the protocol is implanted (e.g., supplemental placement of a rod/screw system or a plate/screw system).

#### 9.4 Device Explant and Retrieval

In the event of a Superior® device removal, the device and the Investigator's written explanation of the event will be sent to the Sponsor following instructions from the Sponsor. The Investigator(s) will also be required to document the failure mode of the device and submit it to the Sponsor.

### 10 Statistical Considerations and Methodology

#### 10.1 Clinical Trial Objective

The objective of this trial is to show that the Superior® Interspinous Spacer is safe and non-inferior in efficacy compared to the X-STOP® IPD® device in patients with moderate lumbar spinal stenosis at 60 months post-treatment.

#### 10.2 Primary Outcome

The *treatment arm* (Superior® ISS) is compared to a control comprising surgical implantation of the X-STOP® IPD® device. The primary efficacy analysis is a responder analysis at 60-months post-op where a subject is a responder if each of the following are satisfied:

- Clinically significant improvement in outcomes compared to baseline, as determined by meeting the following for at least two of three domains of the Zurich Claudication Questionnaire (ZCQ):
  - Improvement in physical function by  $\geq 0.5$  points
  - Improvement in symptom severity by  $\geq 0.5$  points
  - "Satisfied" or "somewhat satisfied" as defined by a score of  $< 2.5$  points on the patient satisfaction domain
- No re-operations, revisions, removals or supplemental fixation at the index level(s)
- No major implant or procedure-related complications defined as:
  - No dislodgement, migration, or deformation
  - No new or persistent worsened neurological deficit at the index level
  - No spinous process fractures
  - No deep infection, death, or other permanent device attributed disability
- No clinically significant confounding treatments:
  - No epidural injections or nerve block procedures at index level, spinal cord stimulators or rhizotomies

### 10.3 Randomization

1:1 for treatment to control. A randomized block design at each site was used.

### 10.4 Analysis Populations

The study contains two treatment arms with patients receiving either the Superior® ISS or the X-STOP® IPD® device. The following subject groups or analysis populations will be used to complete the analysis of data:

*Modified Intent-to-treat* patient population (mITT): The mITT patient population will include all patients randomized, and with an anesthesia start time recorded, where patients will be classified by the group in which they are randomized, regardless of the treatment received.

*Per protocol* patient population (PP): The PP patient population will include all subjects with 60-month follow-up data and no major protocol deviations and subjects that failed before 60 months and subsequently did not complete 60 months.

The primary efficacy analysis will be conducted on the mITT patient population. Secondary efficacy analyses will be done on the PP population. All safety data will be analyzed based on the mITT patient population.

The numbers of patients in the mITT analysis set included 190 patients randomized to Superior® and 201 patients randomized to the X-STOP® IPD® Control group. Eight (8) Superior® patients and 12 X-STOP® IPD patients are from 2 sites that are not participating in the PAS. This reduces the analysis set to 182 Superior® and 189 X-STOP® IPD®, respectively. Assuming 85% follow-up for the primary effectiveness endpoint at Month 60, there will be 155 Superior® patients and 161 X-STOP® IPD patients included in the primary non-inferiority evaluation.

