### 5.2.2 Secondary Endpoints

The secondary endpoints of this investigation are:

- To demonstrate the superiority of Superior® ISS to X-STOP® IPD® in effectively treating moderately impaired LSS patients as measured by 60 months postoperative overall success rates
- VertiFlex® Patient Satisfaction Survey – percent of patients scoring  $\leq 2.5$  on a 4 point scale
- Oswestry Disability Index (ODI) Version 2– compared to baseline, 15 point improvement (reduction in score) is considered clinically significant
- Visual Analogue Scale (VAS) - compared to baseline, an improvement in leg and/or back pain of 20 mm (on a 100 mm scale) is considered clinically significant
- To evaluate generic health status pre- and postoperatively using the SF-12 Short Form Health Survey, Version 2
- To evaluate maintenance of distraction defined by  $\leq 4$  mm of measurable decrease in the posterior disc space height on successive radiographs obtained at 6 weeks and 60 months postoperatively

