## 10.6 Superiority

The following superiority hypotheses will be tested if non-inferiority is demonstrated. By the closed testing principle there is no need for multiplicity adjustment.

**Ho:**  $CCS_{\text{Superior}} - CCS_{\text{X-STOP}} \leq 0$  (not superior)

**Ha:**  $CCS_{\text{Superior}} - CCS_{\text{X-STOP}} > 0$  (superior)

The posterior probability that  $(CCS_{\text{Superior}} - CCS_{\text{X-STOP}}) > 0$  will be determined using Beta(1,1) priors for 5-year  $CCS_{\text{Superior}}$  and for 5-year  $CCS_{\text{X-STOP}}$ . If the posterior probability of superior is at least equal to 0.95, then a superiority claim will be made.

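### The population for the superiority claim is left open: Section 10.4, read literally, sends it to the per-protocol set, while Section 10.6 names none and its place in a closed test suggests mITT

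*Combined protocol and SAP*

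**What the plan says.** - Section 5.2.2 opens its list with "The secondary endpoints of this investigation are" and puts first the superiority of the study device over the control "as measured by 60 months postoperative overall success rates". The protocol summary also lists it first among the secondary endpoints.
- Section 10.4 assigns populations by type of analysis: "The primary efficacy analysis will be conducted on the mITT patient population", and then, with no exception, "Secondary efficacy analyses will be done on the PP population".
- Section 10.4 defines PP as subjects with Month-60 data and no major deviation "and subjects that failed before 60 months and subsequently did not complete 60 months".
- Section 10.6 says "The following superiority hypotheses will be tested if non-inferiority is demonstrated" and "If the posterior probability of superior is at least equal to 0.95, then a superiority claim will be made". It gives priors and a threshold, but no population and no missing-data rule.
- Section 10.7 assigns mITT and Bayesian imputation to the primary analysis. Its tipping point analysis computes only the posterior probability of non-inferiority.

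**The concern.** The superiority test can lead to a claim, so it should have a fixed population that keeps the randomized comparison intact. Two sections point to different sets and nothing settles which governs. If that stays open until the data are in, the choice between mITT and PP can be made with the results in view.

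PP is also a weak base for a claim, because membership depends partly on outcome. A patient who fails early stays in whether or not Month 60 is reached. A patient lost while still failure-free is removed. Section 9.3 reinforces the pattern, since patients with further surgery at the index level are exited and remain in PP as failures. If the arms differ in dropout among failure-free patients, or in early failure, PP success rates can differ when the true rates do not. On the literal reading, superiority would also have neither the imputation nor the tipping point analysis of Section 10.7.

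**Working it through.** **1. What the plan's figures cover.** Follow-up: 0.85 × 182 = 154.7 (155) and 0.85 × 189 = 160.65 (161), as stated in Section 10.4. Non-inferiority power at 40% vs 37.8%, margin 0.10, Beta(1,1) priors and posterior at least 0.95: exact enumeration gives 74.3% and a normal approximation 71.9%, against the stated 73%. The plan gives no operating figure for superiority or for PP. By exact enumeration at 155 and 161, with 40% true success in both arms, the chance of a false superiority claim is 0.055.

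**2. Bias from PP selection.** Assumptions, since the documents give neither early-failure rates nor arm-specific Month-60 dropout: true success p = 0.39 in both arms (about midway between 40% and 37.8%), early-failure share f, dropout m among failure-free patients, and dropout unrelated to later outcome within that group.

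PP rate = p(1 − m) / [f + (1 − f)(1 − m)]

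With f = 0.30 in both arms:
- m = 0.10: 0.351 / 0.93 = 37.7%
- m = 0.20: 0.312 / 0.86 = 36.3%
- Difference: about 1.5 points, with no true difference.

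False-claim rate ≈ 1 − Φ(1.645 − bias/SE), with SE = sqrt(2 × 0.39 × 0.61 / 158) = 5.5 points (158 is the mean of 155 and 161).

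| Dropout, study vs control | Early failure, study vs control | Bias (points) | False-claim rate |
|---|---|---|---|
| 15% vs 15% | 30% vs 30% | 0 | 5% (nominal) |
| 14% vs 16% | 30% vs 30% | +0.3 | 5.6% |
| 10% vs 20% | 30% vs 30% | +1.5 | about 8% |
| 20% vs 10% | 30% vs 30% | −1.5 | about 3% |
| 15% vs 15% | 20% vs 40% | +1.2 | about 8% |

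Last row: 0.3315/0.88 = 37.7% and 0.3315/0.91 = 36.4%; 1 − Φ(1.645 − 1.2/5.5) ≈ 8%.

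**3. Exact check.** With 40% true success in both arms, 182 and 189 patients, and early failure of 20% to 40% (equal in both arms):
- full set, nobody lost: 0.052
- PP, equal dropout of 10% to 20%: 0.046 to 0.054
- PP, dropout 10% vs 20% or 15% vs 25%, higher in control: bias +1.0 to +2.1 points, false-claim rate 0.073 to 0.103
- PP, dropout 20% vs 10%: 0.022 to 0.033

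**4. Does mITT remove the bias?** Take f = 0.30 and dropout 10% vs 20%. The lost shares of the arms are 0.70 × 0.10 = 0.07 and 0.70 × 0.20 = 0.14.
- Imputing from each arm's overall observed rate: 0.351 + 0.07 × 0.377 = 37.7% and 0.312 + 0.14 × 0.363 = 36.3%. These are the PP rates again.
- Imputing from failure-free patients: their observed success is 0.351/0.63 = 0.312/0.56 = 55.7%. Then 0.351 + 0.07 × 0.557 = 39.0% and 0.312 + 0.14 × 0.557 = 39.0%. The bias is gone under the stated dropout assumption.

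Section 10.7 does not say which kind of imputation is meant.

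**The case against.** The strongest case is that mITT was intended for superiority all along. Section 10.2 describes the primary efficacy analysis as a Month-60 responder analysis, and superiority uses the same outcome and priors with only the threshold moved from −0.10 to 0. Section 10.6 follows the primary analysis directly and forms the second step of one closed test. Section 10.7 on missing data comes next. Secondary endpoints have their own Section 10.9, which does not mention the superiority test. On this view, the sentence in Section 10.4 refers to supportive PP analyses. This is a fair reading, and it means the documents do not establish that superiority will be run on PP. It does not close the matter: Section 5.2.2 calls superiority secondary, Section 10.4 makes no exception, and no section places the test on mITT.

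The second objection is to the size. Two-year compliance was 97% and 95%, and the plan assumes 85% in both arms at Month 60. No 10-point dropout gap appears in the documents, and a 2-point gap costs about 0.3 points. This stands: the larger figures illustrate sensitivity and do not predict what will happen.

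A reader might infer that the plan inflates the superiority error to 8% or more and that moving to mITT would cure it. The documents support neither step. The direction of any imbalance is unknown, and under arm-level imputation mITT shows the same expected shift. Nor does using different sets for the two steps by itself break the closed test; the test needs each step to hold its level, which PP selection can disturb.

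**Conclusion.** The point holds as a conflict in the text that leaves the population for a claim undetermined. Read literally, Section 10.4 gives PP; the structure around Section 10.6 suggests mITT. If PP were used, bias could arise in either direction: about 1.5 points for a 10-point dropout gap under the assumed rates, with a false-claim rate of about 8% or about 3% depending on which arm loses more, and none when dropout and early failure are equal between arms. For scale, 1.5 points compares with the 2.2-point difference first assumed for the sample size. These sizes rest on assumed early-failure and dropout rates. The gain from mITT depends on an imputation model that Section 10.7 does not specify.

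It would go too far to require mITT for every secondary endpoint on this ground. Section 10.9 treats them mainly descriptively, attaches no claim to them, and no imputation is defined for them.

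**What to change.** - **Section 10.6:** state that superiority is tested on the mITT set with the same imputation as the primary analysis.
- **Section 10.7:** specify that a missing Month-60 outcome is imputed conditionally on the patient being failure-free at dropout and on the last observed status. Extend the tipping point analysis to the posterior probability of superiority, using the same grid of scenarios.
- **Section 10.4:** except superiority from the sentence on secondary efficacy analyses, and describe PP as supportive for it.

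The cost is a few sentences of text, a written imputation model, and a little more analysis work. No new data are needed. The change should be made before Month-60 outcomes are compared by arm.

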### 10.5 Primary Statistical Analysis

The primary hypothesis of this extended follow-up post approval study is that performance of the Superior® ISS remains clinically non-inferior to X-STOP® IPD® at 5 years post-surgery using the same non-inferiority margin as was used at 2-years. The hypotheses to be tested may be symbolically described as follows:

**H0:  $CCS_{\text{Superior}} - CCS_{\text{X-STOP}} \leq -0.10$  (inferior)**

**Ha:  $CCS_{\text{Superior}} - CCS_{\text{X-STOP}} > -0.10$  (not inferior)**

At 2-years, follow-up compliance was 97% and 95%, and the observed overall success rates were 51.9% (95/183) and 49.7% (93/187) for Superior® ISS and X-STOP® IPD®, respectively. For the purpose of sample size analysis it was initially assumed: a) that at 5-years, follow-up compliance would be 85% in both groups (i.e., 155 Superior® and 161 X-STOP® IPD®); b) a device group difference equal to that observed at 2-years (i.e., 2.2%); and c) at 5-years 40% of Superior® ISS would achieve CCS (and so 37.8% is assumed for X-STOP® IPD®). In keeping with the original design, these hypotheses will be tested by determining the Bayesian posterior probability that  $(CCS_{\text{Superior}} - CCS_{\text{X-STOP}}) > -0.10$ .

If the Bayesian posterior probability is at least equal to 0.95, then the hypothesis that Superior® ISS is non-inferior to X-STOP® IPD® at 5-years will be accepted. Non-informative beta(1,1) priors were assumed for both groups. With these assumptions, power is 73% and type 1 error is equal to 0.05. However, updated Month 36 results reflect a device group difference equal to 5.7%. Conservatively assuming a 5% difference, power increases to 87% and remains above 80% for device group differences larger than about 3.5%.

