
Number of Sites:
	
Only sites participating in the original IDE study will participate in this continued follow-up protocol. 25 IDE sites remain eligible for participation.

Study Enrollment:
	
Enrollment was completed in December 2011, with 391 randomized and treated patients and 28 non-randomized Superior® training patients.

Study Duration:
	
Subjects included in the original clinical investigation (G070118) returned for follow-up visits at 6 weeks, and 3, 6, 12, 18 and 24 months post-treatment to collect data for the primary evaluation of safety and effectiveness. Patients will be followed annually until each patient has reached the 60 month time point. Study duration is approximately 36 months as all patients have reached 24 months prior to the start of this continued follow-up protocol. Patients may potentially be followed annually for up to 10 years as part of a possible post-approval study.

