## 10.7 Missing Data and Loss-to-Follow-Up

In order to best preserve an intent-to-treat philosophy, the primary analysis will be done on the mITT group. Those subjects who withdraw, or who are lost (LTFU) after randomization, will be included in the analysis using Bayesian imputation. This analysis will be the primary analysis, but recognizing that there is no way, statistically, to handle these subjects without possibly introducing bias, a tipping point analysis will be conducted.

The tipping point sensitivity analysis will be conducted in which missing values in each group are separately assumed to be either successes or failures. Treatment group differences will be computed based on all possible combinations of assigning success or failure to the primary overall success endpoint to the patients in the two groups. For example, one scenario will be that all missing Superior device observations are failures and all missing X-STOP observations are successes. The next scenario would have one success and the remaining missing values as failure for Superior and all missing X-STOP as successes. For each scenario, the Bayesian posterior probability of non-inferiority will be determined. These results will be plotted using a dot plot with the number of missings assumed as failures for Superior on the x-axis and the number of missing assumed as failures for controls on the Y-axis. The dots will be color coded to indicate whether or not the primary statistical conclusion changes under each individual scenario. If the fraction of scenarios in which the statistical conclusion changes is small, the primary results will have been shown to be robust against assumptions concerning missingness.

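### Does the primary Beta(1,1) comparison lose worthwhile power by leaving out baseline ZCQ scores?

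*Combined protocol and SAP*

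**What the plan says.** Section 10.5 keeps the method of the earlier study: "In keeping with the original design, these hypotheses will be tested by determining the Bayesian posterior probability that" the difference in success rates exceeds -0.10, with non-inferiority accepted at a posterior probability of 0.95 or more. On the model it says "Non-informative beta(1,1) priors were assumed for both groups". Section 10.6 uses the same structure for superiority, where the posterior probability "will be determined using Beta(1,1) priors for 5-year" success in each arm. No baseline variable enters either test.

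The same section gives 73% power at a 2.2-point difference and 87% at 5 points, and reports that "updated Month 36 results reflect a device group difference equal to 5.7" percent. On numbers, section 10.4 says: "Assuming 85% follow-up for the primary effectiveness endpoint at Month 60, there will be 155" investigational patients, with 161 controls.

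Baseline ZCQ is collected (section 6.5.2). Two of the three ZCQ domains in the responder rule are changes from it (section 10.2). Randomization was blocked within site (section 10.3).

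**The concern.** Baseline physical function and symptom severity are part of the arithmetic of the endpoint, so they could be expected to predict it. Adjusting for a prognostic baseline variable reduces the variance of the treatment difference, and the data already exist. The Protocol Summary states "Enrollment was completed in December 2011, with 391 randomized and treated patients", so further precision can come only from follow-up or from the analysis. Stated power is 73% under the initial assumption and passes 80% only for true differences above about 3.5 points.

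No other section supplies the adjustment. Section 10.7 names no predictors for its imputation, section 10.8 models only treatment and number of levels, and section 10.11 uses baseline severity descriptively. If baseline ZCQ were strongly prognostic, the primary and superiority tests would both be less sensitive than they could be.

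**Working it through.** **Inputs from section 10.5:** success 40% v 37.8% (or 40% v 35% for the 5-point case), 155 and 161 patients, margin -0.10, threshold 0.95, Beta(1,1) priors. From section 10.4: 182 and 189 patients before loss. **Assumed, because the documents are silent:** odds ratio (OR) of success per SD of the mean of the two baseline scores, correlation 0.6 between the scores, between-site SD 0.3 in log-odds, 25 unequal sites, blocks of 4, loss at random.

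**1. The plan's own figures.** Sum the two binomial distributions over all outcomes (x1, x2) for which P(p1 - p2 > -0.10) is at least 0.95, where p1 ~ Beta(1 + x1, 156 - x1) and p2 ~ Beta(1 + x2, 162 - x2).

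- At 155/161: power 74.3% and 88.1%; rejection rate at 27.8% v 37.8% is 5.5%.
- At 154/162: power 71.3% and 86.3%.
- Averaged over random 85% retention: 72.5% and 87.1%.

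Normal check at 2.2 points: SE = sqrt(0.40 x 0.60/155 + 0.378 x 0.622/161) = 0.05485; 0.122/0.05485 - 1.645 = 0.579; power 71.9%. At 5 points: SE = 0.05442; 0.15/0.05442 - 1.645 = 1.111; power 86.7%. The stated 73% and 87% are sound.

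**2. What a variance reduction v would buy.** Replace SE by SE x sqrt(1 - v); the equivalent sample is 316/(1 - v). At 2.2 points:

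- v = 2.1%: power 72.7% (+0.8), about 7 patients.
- v = 5.3%: 73.9% (+2.0), about 18 patients.
- v = 9.2%: 75.5% (+3.6), about 32 patients.

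**3. Simulated adjustment.** Bayesian logistic model with treatment, both baseline scores and a site intercept, standardised to the risk difference; 12,000 trials per cell, retention varying:

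| OR per SD | Variance change | 40% v 37.8%: pooled, adjusted | 40% v 35%: pooled, adjusted |
|---|---|---|---|
| 1.0 | -0.1% | 72.2, 71.9 (-0.3) | 87.1, 86.8 (-0.3) |
| 1.2 | -0.8% | 72.8, 72.6 (-0.2) | 86.4, 86.6 (+0.2) |
| 1.35 | -2.1% | 72.5, 72.7 (+0.2) | 87.5, 87.8 (+0.3) |
| 1.65 | -5.3% | 72.4, 73.8 (+1.4) | 87.9, 88.8 (+0.9) |
| 2.0 | -9.2% | 73.0, 76.1 (+3.1) | 87.2, 89.9 (+2.7) |

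The paired differences have standard error 0.1 to 0.3 points, so up to OR 1.35 the effect is practically zero. Type 1 error is 4.8-5.6% pooled and 4.7-5.5% adjusted. A site term alone leaves the variance unchanged (ratio 1.00) and costs 0.4 points. For superiority at 40% v 35%, power moves from 23.4% to 23.5% at OR 1.35 and from 23.1% to 23.6% at OR 1.65.

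A different adjusted analysis, with ZCQ only and averaged over nearby arm sizes, is somewhat more favourable: about 0 at OR 1, +0.4 to +0.6 at 1.3, +1.2 to +1.6 at 1.5 and +2.5 to +3.7 at 2.0.

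**4. Which OR is credible?** Simulating the section 10.2 rule itself, with assumed score distributions and 30% failing for non-ZCQ reasons, gives OR 1.67, 1.49, 1.30 and 1.08 at baseline-to-Month-60 correlations of 0.3, 0.5, 0.7 and 0.9. With Month-60 spread 1.5 times baseline it gives 1.32, 1.12 and 0.91 at 0.3, 0.5 and 0.7. Power changes at 2.2 points on such data were +1.4, +0.7 and +0.1 (correlations 0.3, 0.5, 0.7) and -0.5 (correlation 0.5, wider spread). OR 2.0 was not reached.

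**5. At the 155/161 the plan names.** The site-and-ZCQ model changes power by -2.2, -1.5 and +0.1 points at OR 1, 1.35 and 1.65 (2.2-point difference), and by -1.7, -1.0 and +0.2 (5-point difference). This is largely a lattice effect: the Beta(1,1) rule happens to do well at that split, which may not be the final one. It still means no improvement is demonstrated at the planned size.

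**The case for a change.** The best case for adjustment is that it is cheap. The covariates are in hand, type 1 error stays near 5%, and at OR 1.65 the gain is worth about 18 patients: (316 + 18)/371 = 90% follow-up in place of 85%. If ZCQ is not prognostic, the average loss is only 0.3 to 0.6 points. The model could be standardised to the risk difference so that the -0.10 margin still applies.

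That stands as a conditional statement: if baseline ZCQ were clearly prognostic, adjustment would add a point or more. But nothing in the documents establishes the condition, and several features weaken the link. Entry required a physical function score of at least 2.0, satisfaction has no baseline value, and reoperation, listed complications or injections mean failure whatever the ZCQ.

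The change also has costs. It would replace the primary model after Month 24 and Month 36 between-arm results were known, and would add priors and standardisation choices. It also fits poorly with the section 10.7 tipping-point grid: "Treatment group differences will be computed based on all possible combinations of assigning success or failure to the primary overall success endpoint". That grid is indexed by counts (with 27 and 28 missing, 28 x 29 = 812 scenarios). Under an adjusted model it also matters which patients are set to success, so the grid would have to stay on Beta(1,1) while the primary test moved elsewhere. Offering the adjusted model as supportive only avoids this, but leaves the power of the primary test unchanged.

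Patients lost to follow-up "will be included in the analysis using Bayesian imputation", by a model that is not described. It might already use ZCQ. How fully that imputation should be specified is a separate question.

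**Conclusion.** No defect. The unadjusted Beta(1,1) test is a valid analysis of a randomized comparison. Its rule, prior, margin and threshold are stated, its power reproduces to within about 1.5 points, and its type 1 error is near 5% (section 5.3 itself says approximately). Leaving out baseline ZCQ biases nothing.

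Over the ORs that the endpoint rule produced (0.91 to 1.67), adjustment moves primary power by roughly -0.5 to +1.5 points averaged over retention, and by about -2 to 0 at exactly 155/161. A gain near 3 points needs an OR of about 2.0, which nothing in the documents supports. These figures rest on assumed prognostic strength, site variation and random loss. The conclusion that the planned test is valid does not depend on the assumed prognostic strength.

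Keeping the 2-year method is the plan's stated choice and a reasonable one for a study asking whether non-inferiority persists under the same margin. No change is needed.
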